6. STUDY POPULATION

a. Population (base)

Sixteen PT practices will participate. All practices comprise at least two physiotherapists of whom at least one is specialized in geriatrics, as evidenced by a professional degree.

During the study, data will be collected from community-dwelling older adults (≥ 70 years) who visit the PT practice due to mobility problems related to activities of daily living. In addition, potential participants must have a sedentary lifestyle or must be at risk of losing an active lifestyle in the near future (as rated by the participant, relatives, or a referring physician).

b. Inclusion criteria

All older adults from 70 years or older who are referred to the physiotherapist are included in this study. However, not all older adults will be followed for the full duration of the study. Only those who are community-dwelling, have mobility related problems or problems related to activities of daily living and have a sedentary lifestyle or are at risk of losing an active lifestyle in the near future are eligible for follow-up. Only clinical data is obtained from the participants who are not eligible for follow-up to control for selection bias.

Eligible for separate analysis:

- Patients with problems understanding advises and/or communicating with the professional due to Dutch language problems and/or mild dementia are not excluded, because we think that the Coach2Move approach will be adequate because of the focus on contextual resources.

c. Exclusion criteria

A potential subject who meets any of the following criteria will be excluded from participation in this study:

- Patients who are not ambulatory after treatment and/or are in palliative phase.
- Patients who are indicated to become institutionalised in the near future.

d. Sample size calculation

Primary endpoints are TUG and LAPAQ at 6 months, and the combined objective of this trial is to show that one of these improves while the other does not deteriorates [13]. With the Stepped Wedge design as below (4 groups of 4 practices with 5 patients in each of 5 measurement periods and none in the implementation period, so 400 patients in total), a simulation study shows that the SE (standard error) is $0.21 \times SD$ for each endpoint when the ICC = 0.10 (regardless of the size of the effect due to the linearity of the analysis model).

Figure 1. Depiction of proposed stepped-wedge, cluster randomized design.						
	3 months	6 months	9 months	12 months	15 months	18 months
Group 1 (Practices 1,2,3,4)	Control	Imp + WO	Intervention	Intervention	Intervention	Intervention
Group 2 (Practices 5,6,7)	Control	Control	Imp + WO	Intervention	Intervention	Intervention
Group 3 (Practices 8, 9,10)	Control	Control	Control	Imp+ WO	Intervention	Intervention
Group 4 (Practices 11,12,13)	Control	Control	Control	Control	Imp+ WO	Intervention

Abbreviations: Imp +WO = Implementation and wash-out period.

Then applying the method as described by Donkers et al. with the following design parameters [13]:

- TUG: relevant effect: 1.4 seconds; SD=2.0 seconds; non-inferiority margin= 0.4 seconds, so $SE=0.21*2=0.42$; [14]
- LAPAQ: relevant effect: 15 minutes; SD=30 minutes; non-inferiority margin=5 minutes, so $SE=0.21*30=6.3$; [15]
- Correlation between TUG and LAPAQ is low (correlation of -0.4 etc found, so we assume correlations of the stepped wedge estimates of no more than +0.3; [16] yields that the power for the combined objective is >80% (actually 86%).

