4. STUDY DESIGN

To assess the cost-effectiveness of Coach2Move compared to usual physiotherapy care, we will use a stepped wedge cluster randomised trial design. A stepped wedge study has several advantages over RCTs: it allows evaluating as well as implementing a new promising intervention (Coach2Move) versus regular care in real-life setting and minimizes nonparticipation and contamination.

In this study 16 physiotherapy practices will be included. The 16 practices will be divided into 4 clusters (4-4-4-4). Each practice will include at least 25 patient during the entire duration of the study, which means a minimum number of 400 (16x25) patients will be included. Per cluster four months are planned for implementation of Coach2Move, from which one month is incorporated to serve as a wash-out period between the control and implementation phase (thus resulting in 15 months of data in all practices) (please see Figure 1 for a visual depiction). During the wash-out and implementation period in a cluster, included patients will not be measured. In total, this should generate approximately 200 participants in the control group and 200 participants in the intervention group.

Control group is defined as all patients who meet the inclusion criteria and signed informed consent, who were treated in the indicated practices by participating therapists prior to the Coach2Move education of those therapists, whereas the intervention group is defined as all eligible patients who were treated after the Coach2Move education of the therapists. In other words, the control group receives regular physiotherapy, whereas the intervention group receives physiotherapy conform Coach2Move strategy.

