4. First assessment at the start of the intervention (t0) in which a number of measures will be performed. Questionnaires: LAPAQ, EQ-5D, EFIP, PSC and CIRS-G. In addition, the modified TUG is carried out. This assessment will take approximately 60 minutes and is carried out by one of the researchers during the control period or by one of the participating PT(G)'s during the intervention period.
5. Physiotherapy treatment. In either the experimental or the control group, the physiotherapist determines the number of physiotherapy consults that are needed. This is common in physiotherapy. During the intervention period, the patient and the PT(G) will choose the best fitting intervention profile together.
6. The second assessment (t1) at three months after the start of the intervention: questionnaires: LAPAQ, EQ-5D, EFIP, PSC, GPE and healthcare utilization. Again, the modified TUG is carried out. This assessment will take approximately 45 minutes.
7. The third assessment (t2) at six months after the start of the intervention. Questionnaires: LAPAQ, EQ-5D, EFIP, PSC, GPE, healthcare utilization and adherence. The modified TUG is performed. This assessment will also take approximately 45 minutes and is carried out by the researcher.
8. The fourth assessment (t3) at twelve months after the start of the intervention. Questionnaires: LAPAQ, EQ-5D, EFIP, PSC, GPE, healthcare utilization and adherence. The modified TUG is carried out once again. This assessment will also take approximately 45 minutes and is carried out by the researcher.

A randomised selection of participants is asked to join in focus group meetings to share experiences on Coach2Move. Participation is voluntarily.

All participants will be debriefed after the study by sending an information brochure concerning the most important outcomes and conclusions of the study. In addition, the participating practices for physiotherapy will be sent the same information in flyer format, which they can hang in a visible spot in their practice. Dutch magazines and newspapers will be approached to publish the research outcomes, as has happened during the previous trial of Coach2Move.

Procedure of enrolled therapists in the study:

1. Start with physiotherapeutic care as usual.
2. Electronic medical record (EPD) will be provided to support clinical reasoning and monitoring the process.

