3. Intake is performed by the PT(G), alongside of an extensive intake carried out researcher of Radboudumc during the control period. During the intervention period, the PT(G) is charged with the extensive intake.
4. Web-based e-learning on Coach2Move
5. Coach2Move introduction through a two-day education program
6. Extensive physiotherapeutic intake under supervision of a researcher
7. Peer assessment meetings
8. Physiotherapeutic treatment conform Coach2Move approach
9. Physiotherapeutic intake takes place without presence of a researcher.
10. Focus groups on process evaluation of implementation

d. Withdrawal of individual subjects

Participating patients can leave the study at any time for any reason if they wish to do so without any consequences. Treatment will be continued accordingly. This means that during the control period physiotherapeutic treatment will be continued corresponding regular care, whereas during the intervention period treatment will be continued conform Coach2Move strategy, since Coach2Move will be provided to all patients. The investigator can decide to withdraw a subject from the study for urgent medical reasons. Their collected data however, will still be analysed.

Participants suffering from dementia will be treated according to the Code of conduct: incapacitated elderly. In consultation with their informal caregiver, the choice could be made to withdraw from the study.

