Data analysis to determine the overall effectiveness strategy subsequently involves comparison of the data points in the control section of the wedge with those in the intervention section. Because of the hierarchical design (patients nested within practices or within therapists), multilevel linear and logistic regression analysis will be used to compare the outcomes between treatment groups, with age, sex, comorbidity, frailty level and physical functioning at baseline at the patient level as covariates[13]. Time will be included as a fixed effect according to Donkers et al. [13]. In addition, subgroup analyses will be performed between PT and PTG levels.

c. Other study parameters

Qualitative Data Analysis

Interviews and focus group discussions will be elaborated verbatim (every word captured exactly, each final anonymised transcript will be added to the analysis). A structured thematic approach will be used to analyse the qualitative data.

The analysis will consist of five steps: 1) familiarization and initial coding line by line by two researchers; 2) developing a consolidated codebook; 3) coding and indexing all transcripts against the consolidated codebook, and discussion in the research group to focus on key findings for each study objective; 4) charting overall findings and look at any differences in patients, practices and context in dialogue with the project group and patient panel; 5) synthesis and drawing conclusions. In the analysis phase, descriptive summaries of interview data will be produced presenting the data per practice to help identify patterns.

Synthesizing quantitative and qualitative results:

An overall synthesis of the findings of the process evaluation study will take place to describe the context, the implementation of the intervention and the mechanisms of impact, with the aim of explicating the main trial findings and interrogating the intervention theory. Where data is available, we will test hypotheses based on qualitative analysis quantitatively. We will also, where appropriate, conduct the reverse operation and use quantitative data to focus qualitative analyses. Where data from different sources provide competing narratives or findings, we will make these explicit when reporting and provide a justification of our interpretation in such differences.

Budget Impact Analysis (BIA):

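### The 86% power assumes that all 400 patients give a 6-month outcome, and baseline LAPAQ, already collected for the less well-powered primary endpoint, is not a named covariate

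*Combined protocol and SAP*

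**What the plan says.** Section 6.d takes TUG and LAPAQ at 6 months as primary endpoints. It bases power on "4 groups of 4 practices with 5 patients in each of 5 measurement periods", 400 in all, with an SE of 0.21 × SD at an ICC of 0.10, and concludes that "the power for the combined objective is >80% (actually 86"%). Section 4 gives the same number as the recruitment floor: "a minimum number of 400 (16x25) patients will be included". No loss rate or inflation factor appears. Section 8.d says "Participating patients can leave the study at any time for any reason".

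Section 9.b specifies multilevel regression "with age, sex, comorbidity, frailty level and physical functioning at baseline at the patient level as covariates", with no instrument attached to physical functioning. Section 8.c lists the T0 measures as "Questionnaires: LAPAQ, EQ-5D, EFIP, PSC and CIRS-G", plus the modified TUG. It adds that this first assessment "is carried out by one of the researchers during the control period or by one of the participating" therapists during the intervention period. Follow-up is measured by the researchers (section 7.b).

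**The concern.** The number recruited at minimum and the number analysed in the power calculation are both 400, so the calculation leaves no stated room for missing 6-month outcomes. The patients are aged 70 or over and may withdraw freely. A reader cannot tell how much loss the power claim can absorb.

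The covariate list also leaves the primary model open. The plan presents LAPAQ as a measure of physical activity and TUG as one of functional mobility (section 8.a), so baseline physical functioning does not plainly include baseline LAPAQ. An outcome's own baseline is usually a strong candidate for reducing residual variance, and here it costs nothing to collect. Left open, its use could be settled after the data are seen.

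**Working it through.** **Inputs (section 6.d).** 16 practices in 4 groups; 5 patients per practice in each of 5 measured periods; implementation period empty; ICC 0.10. TUG: effect 1.4 s, SD 2.0, margin 0.4, SE 0.42. LAPAQ: effect 15 min, SD 30, margin 5, SE 6.3. Correlation of the two estimates +0.3. Success means superiority on one endpoint and non-inferiority on the other. Assumed, because not stated: one-sided 0.025 for every test.

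**1. SE.** Generalised least squares on practice-period means (fixed periods, random practice intercept, cell variance 0.9/5 plus practice variance 0.1) gives 0.213 × SD. The plan's 0.21 is confirmed.

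**2. Power.** Standardised distances beyond the critical value:
- TUG superiority: 1.4/0.42 − 1.96 = 1.37 (91.5%)
- LAPAQ superiority: 15/6.3 − 1.96 = 0.42 (66.3%)
- TUG non-inferiority: 1.8/0.42 − 1.96 = 2.33 (99.0%)
- LAPAQ non-inferiority: 20/6.3 − 1.96 = 1.21 (88.8%)

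Joint power = P(TUG superior, LAPAQ non-inferior) + P(LAPAQ superior, TUG non-inferior) − P(both superior) = 0.824 + 0.660 − 0.625 = 85.8%. This reproduces 86%. Superiority at 0.0125 with non-inferiority at 0.05 gives 86.7%, so the stated power does not identify the alpha used.

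**3. Loss (rates assumed, spread evenly).** Cell size becomes 5 × (1 − d). No covariate gain:

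| Loss | SE multiplier | Joint power |
|---|---|---|
| 0% | 1.000 | 85.8% |
| 10% | 1.049 | 81.8% |
| 15% | 1.076 | 79.5% |
| 20% | 1.106 | 76.8% |

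Power reaches 80% at 13.9% loss with SE 0.21, or 10.9% with the unrounded 0.213.

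**4. Planned covariates (correlations assumed).** Multiply patient-level variance by (1 − R²) and leave practice variance unchanged. With R = 0.5 for TUG and 0.3 for LAPAQ, joint power is 90.1% complete and 82.6% at 20% loss. It reaches 80% at 25.2% loss (SE 0.21) or 22.6% (0.213).

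**5. Adding T0 LAPAQ (TUG R held at 0.5).**

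| LAPAQ R | LAPAQ SE (min) | LAPAQ superiority | Joint, complete | Joint, 20% loss |
|---|---|---|---|---|
| 0.3 | 6.04 | 70.0% | 90.1% | 82.6% |
| 0.4 | 5.82 | 73.1% | 91.9% | 85.0% |
| 0.5 | 5.53 | 77.4% | 94.0% | 88.0% |
| 0.6 | 5.14 | 83.1% | 96.3% | 91.5% |

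For LAPAQ precision, moving from 0.3 to 0.5 is worth 400 × 0.91/0.75 = 485 patients, that is 85 more.

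**6. Assessor shift in T0 LAPAQ.** Bias in the adjusted effect is about −slope × shift. At slope 0.5 (assumed), therapists recording 5 or 10 minutes higher gives −2.5 or −5 minutes. A patient-level simulation (1,500 runs, Monte Carlo SE about 0.15) gave −2.5 and −4.9, against −0.3 with no shift. At R = 0.5:
- 5-minute shift: root-mean-square error √(5.53² + 2.5²) = 6.07, no better than 6.04 without T0 LAPAQ. Joint power is 87% if therapists record higher.
- 10-minute shift: √(5.53² + 5²) = 7.45, with joint power 76% if they record higher.
- If therapists record lower, one-sided type I error for LAPAQ superiority rises from 2.5% to 6.6% (5 minutes) or 14.6% (10 minutes).

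**7. Table check.** The table in section 6.d lists 13 practices (4-3-3-3). The same calculation with 13 gives SE 0.229 × SD and joint power 78.0% before any loss.

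**The case against.** **The T0 adjustment could do harm.** Assessor changes with treatment condition, so an assessor difference in T0 LAPAQ goes straight into the adjusted effect, and step 6 shows that it can cost more than it gains. This stands as a real downside. It does not defeat the change: the plan already adjusts for baseline patient measures, the size of any shift is as undocumented as the correlation, and reporting with and without T0 exposes the problem. T0 TUG is taken at the same split-assessor visit, so the paired reporting must cover both endpoints.

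**No underpowering is shown.** This stands. A reader might infer from step 3 that the trial falls below 80%. The documents give no loss rate, 400 is a minimum and not a cap, and the planned covariates may offset the loss.

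**LAPAQ superiority power of 66% is not the trial's power.** Also correct. Success can come through TUG superiority (91.5%) with LAPAQ non-inferiority (88.8%). The 66% shows only where added precision helps most.

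**Exclusion after recruitment.** One exclusion reads "Patients who are not ambulatory after treatment and/or are in palliative phase". A reader might take this as removing enrolled patients. The list governs potential subjects, so I rest nothing on that reading.

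**Alpha and SD type.** Section 6.d applies a cited method that may fix alpha. If the SDs are already residual, the covariate gains in steps 4 and 5 are partly or wholly double-counted. The gains are therefore conditional.

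**Conclusion.** The 86% is not an arithmetic error. It is a complete-data figure whose analysed number equals the recruitment floor. On the stated SEs and one-sided 0.025, it tolerates about 11–14% loss without covariate gain and about 23–25% under the assumed planned-covariate correlations. The documents do not support a conclusion that the trial is underpowered.

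What holds is a low-cost improvement to the primary model. Baseline LAPAQ is collected but not named, and its use now depends on how physical functioning is read. With LAPAQ R rising from 0.3 to 0.5, the SE falls by about 8% (6.04 to 5.53 minutes) and joint power rises by 4 points with complete data, or from 83% to 88% at 20% loss. These gains assume total SDs, unchanged practice variance and no assessor shift. Confidence is moderate, because neither the correlations nor the loss rate can be fixed from the documents.

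**What to change.** 1. **Section 9.b.** Adjust each 6-month primary outcome for its own T0 value, alongside the covariates already listed: modified TUG in the TUG model and T0 LAPAQ in the LAPAQ model. Say which instrument represents physical functioning.
2. **Section 9.b.** Prespecify and report both primary outcomes with and without their own T0 value, and interpret a material difference as possible assessor bias.
3. **Section 6.d.** State that 86% assumes 6-month outcomes on all 400 patients. Give about 82% at 10% loss and 77% at 20% as illustrations conditional on the stated SEs and the assumed alpha. State alpha and sidedness for each test, and whether the SDs are total or residual. The recruitment target need not change.
4. **Section 6.d, separate point.** Reconcile the 13-practice table with the 16 practices in the text.

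The cost is wording, one parameter in the LAPAQ model and one paired sensitivity analysis per primary outcome, with no new data or patients. The downsides are that the quoted power looks less favourable once loss is shown, and that T0 LAPAQ exposes the estimate to the assessor difference. At slope 0.5, a 10-minute shift produces a bias as large as the whole 5-minute LAPAQ non-inferiority margin.

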7. INVESTIGATIONAL PRODUCTS

a. Coach2Move

The intervention consists of geriatric physiotherapy conform the Coach2Move approach. Coach2Move is a personalized coaching strategy for physiotherapists to elicit physical activity in elderly patients who visit their physiotherapist for mobility problems. This approach helps the PT(G) in clinical reasoning by providing an extensive, pre-structured and systematically organised diagnostic protocol based on the HOAC-II and ICF [7-9]. The diagnostic phase requires more time (60 minutes) than the conventional physiotherapy intake (30 minutes), during which not only impairments and disabilities, but wishes, barriers and facilitators both intrinsic as well as in the context considering physical functioning are profoundly examined. Motivational interviewing is used to find and deal with barriers for becoming physically active and shared decision-making in goal setting.

Physiotherapy conform the Coach2Move strategy is patient focused (tailor made) and goal-oriented. The PT(G) coaches the patient and the environment in reaching and maintaining his/her own goals (self-management).

Another key element of Coach2Move is the knowledge of result among patients. By repeating the measurements conducted at baseline on regular basis (every 6 weeks) and give feedback on the outcomes, patients are aware of the consequences a physical active lifestyle has on their health status. A positive change over time is most likely to increase the adherence of staying physically active.

Based on the extensive intake and in consultation with the patient, a stratified intervention is chosen by picking the best fitting option out of the three patient-tailored intervention profiles with a predefined number of intervention sessions. These profiles have been drawn up to guide the progress throughout the treatment.

These three patient-tailored intervention profiles are defined as follows:

1. Intervention Profile 1 (maximum of five sessions).

Population: Physically inactive older adults with minimal not hindering physical constraints to become (more) physically active.

Intervention: Coaching on self-management and the environment to increase physical activities.

2. Intervention Profile 2 (maximum of eleven sessions).

Population: Older adults with minor or acute mobility problems who can train safe at their own, recovery expected within 2 months.

Intervention:

- (1) Temporary physical therapy intervention to overcome barriers to become (more) physically active (e.g. training of strength, endurance, flexibility or balance, fear reduction, involving social environment, adaptation to personal factors, advising walking aids, etc.).
- (2) Coaching on self-management to become and stay more physically active.

3. Intervention Profile 3 (maximum of eighteen sessions).

Population: Older adults with moderate-to-severe mobility problems and specific problems in activities and participation.

Intervention:

- (1) Supervised physical therapy intervention aimed at decreasing mobility problems and problems in activity and participation and risk on falling.
- (2) Temporary physical therapy intervention to overcome barriers to become (more) physically active (e.g. training of strength, endurance or balance, fear reduction, involving social environment, advising walking aids, etc.).
- (3) Coaching on self-management to become more physically active.

Similarities with usual care physiotherapy: use of physical therapy modalities (such as training of strength, endurance, balance, flexibility, functional training, etc.).

Contrast with usual care physiotherapy: using an extensive intake based on a decision algorithm (clinical reasoning) with an analysis of disabilities and abilities, using motivational interviewing, shared decision-making in setting meaningful goals on increasing (adherence for) physical activity, enhancing self-efficacy and self-management, regular measurements and giving feedback on progress, using personal and environmental factors, using intervention profiles with a predefined number of consults (based on expected recovery), and intervention given by a PT(G) with additional education in Coach2Move.

A process analysis has shown that the Coach2Move strategy differed from usual care physiotherapy in almost all physiotherapeutic phases, but the main contrast was defined by a more patient-centered problem analysis and the use of inspiring goals based on shared decision-making, leading to greater adherence and self-management [17]. In a recent international study it was also recognized that patient-centeredness of guidelines should be increased, which resulted in 14 recommendations including patient-centered intervention goals, use of the ICF terminology in problem analysis, adopting a shared decision-making method, and incorporating patient-reported health outcome measures, elements present in the Coach2Move strategy [18]. These key elements are part of the shift from a biomedical to a biopsychosocial perspective on health: defining health as the ability to self-manage and adapt, with not only a focus on illness and interventions, taking into account strengths rather than weaknesses [19]. Although appreciated, this concept requires substantial personal input, of which not everyone is capable of. Although patients are focused on a broad concept of health (especially the elderly), physicians (including PTs) assess health from a more narrow and biomedical standpoint [20]. So the transfer from a biomedical to a biopsychosocial approach seems to be challenging but necessary for successful treatment results [21].

For participants suffering from (mild) dementia, a social chart will be composed consisting of relevant persons and institutions, so participants are able to receive contextual support instead of intrinsic motivations and personal responsibility in the achievement of set goals.

b. Implementation

Initially, all participating practices of physiotherapy treat the subjects by usual care. At some point in time (selected at random) during the Implementation and wash-out period, Coach2Move is introduced through a two-day education program and two peer assessment meetings. In the control period, physiotherapeutic care will take place as usual. To make sure there is no interference in the treatment due to the study, eligible patients are visited by the researcher within 1 week of registration. In that visit, tests and questionnaires are performed which are not included in usual care. During the implementation period, the extensive intake will be carried out under supervision by a researcher of Radboudumc. This is to ensure all necessary tests are performed.

Furthermore, it is focussed to guarantee objectivity. Lastly, the PT(G) can be coached and receive feedback to optimize the intake. After the implementation phase, the PT(G) is expected to perform the extensive intake on his or her own without the presence of a researcher. The follow-up measurements are being conducted by the researchers of Radboudumc.

The PT(G) is educated in the Coach2Move strategy in a baseline training of 2 days. The education consists of one physical meeting and a web-based e-learning. This education will focus on:

- Setting priorities in physiotherapy treatment by using an algorithm that emphasizes clinical reasoning.
- Making shared decisions on meaningful treatment goals focused on dissolving barriers exercises, and increasing physical activity.
- Making SMARTI focused goals.
- Focusing on coaching and self- management among patients to increase long-term results.
- Working patient-centered.
- Improving motivational interviewing skills.
- Gaining skills for adequate coordination with other involved formal and informal caregivers.
- Using appropriate measurement instruments in the diagnostic phase but also in the evaluation of the intervention and as feedback instrument for the patient and therapist.

In addition to the e-learning, three meetings will be planned in which peer assessment among participating physiotherapists takes place. Peer assessment is an effective way to improve adherence to new guidelines and approaches. Personal feedback and awareness of professional performance are known to be effective in improving the implementation of new strategies [22]. Moreover, insight into the electronic medical record (EPD) will be provided to researchers to support the clinical reasoning and patient involvement and monitoring process and to stimulate communication with the local care network if available.

c. Comparative arm:

In this study, all participating PT practices will serve as their own control. Initially, all 16 practices will provide their usual PT care. No instructions will be given on treatment content, frequency and/or duration of the treatment episode.

